#### 5.4.1.1 Definition of endpoint(s)

Key secondary endpoints will be to evaluate CZP plasma concentrations over the duration of study and treatment emergent SAEs and AEs leading to withdrawal from the time of the first CZP dose through the SFU Visit.

#### 5.4.1.2 Main analytical approach

##### 5.4.1.2.1 CZP plasma concentrations over the duration of study

Individual plasma concentrations of CZP (from conventional venous sampling) will be listed for PKs and will include the actual and nominal sampling times. Any samples that are obtained outside the tolerance window permitted at the specified time point will be discussed at the DEM and any

possible exclusion from any specific analyses (i.e. summary statistics table and geomean figure) will be documented accordingly. If deemed appropriate, the analyses of the summary stats table and geomean figure may be repeated with and without the specific samples affected.

The PK plasma concentrations of CZP will be summarized nominal sampling times by MTX use at screening (same definition in [Section 6.1.1](#)) using descriptive statistics (number of available observations (n), arithmetic mean, median, SD, minimum, maximum, geometric mean, geometric CV and 95% CI for the geometric mean (assuming lognormally distributed data)). Values below the LLOQ will be reported with a clear sign indicating that they were below the LLOQ.

Geometric mean profiles of plasma concentrations for CZP over time will be presented in both linear and semi-logarithmic scale. For the linear scale plot only, the lower and upper 95% confidence interval (CI) for the geometric mean will be displayed.

All plasma concentration figures will include the LLOQ on the semi-logarithmic scale plots and will be based on scheduled times and grouped by MTX use at screening.

Further PK data handling rules are described in [Section 5.3.2](#).

#### **5.4.1.2.2 Treatment-emergent SAEs**

A treatment-emergent adverse event (TEAE) is defined as events that have a start date on or following the first administration of study treatment in RA0138 through the final administration of study treatment+70 days through SFU visit. The treatment-emergent serious adverse event (TESAE) will follow the same definition and also mark serious adverse event as “Yes” in the adverse events CRF form.

The analysis for secondary endpoint for treatment-emergent SAEs will be included as follows:

- Incidence of treatment-emergent SAEs
- Incidence of treatment-emergent SAEs by Maximum Intensity
- Incidence of treatment-emergent SAEs by Maximum Relationship

Serious AEs summaries will be ordered by alphabetical SOC, HLT and decreasing frequency of PT within SOC in the CZP column for tables including event counts.

A listing will be presented for SS for treatment-emergent SAEs. This will include the SOC, HLT and PT, onset date/time and outcome date/time of the event (including relative days), the AE duration, pattern of event, serious/intensity, relationship, action taken and outcome. In addition, the listing will flag hospitalization, SAEs, and AE of special interest.

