8.3.1 Time period and frequency for collecting AE and SAE information

All AEs and SAEs will be collected from the signing of the ICF until the SFU visit as specified in the Schedule of Activities (Section 1.3).

In order to ensure complete safety data collection, all AEs occurring during the study (ie, after the signing of the ICF), including any pretreatment and posttreatment periods required by the protocol, must be reported in the CRF even if no study medication was taken but specific study procedures were conducted. This includes all AEs not present prior to the initial visit and all AEs that recurred or worsened after the initial visit.

All SAEs will be recorded and reported to the Sponsor or designee within 24 hours, as indicated in Appendix 3 (Section 10.3). The Investigator will submit any updated SAE data to the Sponsor within 24 hours of it being available.

The Investigator is specifically requested to collect and report to UCB (or its representative) any SAEs (even if the Investigator is certain that they are in no way associated with the study medication), up to 70 days from the end of the study for each participant, and to also inform participants of the need to inform the Investigator of any SAE within this period. Serious AEs that the Investigator thinks may be associated with the study medication must be reported to UCB regardless of the time between the event and the end of the study.

The method of recording, evaluating, and assessing causality of AE and SAE and the procedures for completing and transmitting SAE reports are provided in Appendix 3 (Section 10.3).

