9.3 Planned safety and other analyses

Safety will be assessed using the SS. Pharmacokinetics and immunogenicity will be assessed using the PKS.

All safety endpoints will be analyzed using descriptive statistics. Safety summaries will include presentations of AEs, laboratory values, and vital signs.

Adverse events will be coded according to the Medical Dictionary for Regulatory Activities. Treatment-emergent AEs will be defined as events that have a start date on or following the first administration of study treatment in RA0138 through the final administration of study treatment +70 days.

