- The Investigator will use clinical judgment to determine the relationship.
- Alternative causes, such as underlying disease(s), concomitant therapy, and other risk factors, as well as the temporal relationship of the event to study medication administration will be considered and investigated.
- The Investigator will also consult the Investigator's Brochure and/or Product Information, for marketed products, in his/her assessment.
- For each AE/SAE, the Investigator **must** document in the medical notes that he/she has reviewed the AE/SAE and has provided an assessment of causality.
- There may be situations in which an SAE has occurred and the Investigator has minimal information to include in the initial report to UCB. However, **it is very important that the Investigator always make an assessment of causality for every event before the initial transmission of the SAE data to UCB.**
- The Investigator may change his/her opinion of causality in light of follow-up information and send an SAE follow-up report with the updated causality assessment.
- The causality assessment is one of the criteria used when determining regulatory reporting requirements.

Follow-up of AEs and SAEs

- The Investigator is obligated to perform or arrange for the conduct of supplemental measurements and/or evaluations as medically indicated or as requested by UCB to elucidate the nature and/or causality of the AE or SAE as fully as possible. This may include additional laboratory tests or investigations, histopathological examinations, or consultation with other health care professionals.
- An AE should be followed until it has resolved, has a stable sequelae, the Investigator determines that it is no longer clinically significant, or the participant is lost to follow-up. This follow-up requirement applies to AEs, SAEs, and AEs of special interest.
- If a participant dies during participation in the study or during a recognized follow-up period, the Investigator will provide UCB with a copy of any post-mortem findings including histopathology.
- New or updated information will be recorded in the originally completed CRF.
- The Investigator will submit any updated SAE data to UCB within 24 hours of receipt of the information.

Reporting of SAEs

SAE Reporting to UCB via an Electronic Data Collection Tool

- The primary mechanism for reporting an SAE to UCB will be the electronic data collection tool.

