### 5.5.1.3 Adverse Events

Adverse events will be recorded from the time of informed consent until study completion. All AEs will be coded and categorized by relationship to CZP. The definitions of TEAE can be found in [Section 5.4.1.2.2](#).

The number and percentage of study participants who experience TEAEs will be for all study participants, SOC, and PT, based on the SS (unless otherwise stated).

Summaries of TEAEs will include the following:

- Summaries of TEAEs will include the following:
  - Incidence of TEAEs (overview including number and percentage of study participants with any TEAEs, serious TEAEs, discontinuations due to TEAEs, drug related TEAEs, severe TEAEs and deaths; event counts will also be included)
- Incidence of TEAEs
- Incidence of TEAEs by maximum relationship
- Incidence of TEAEs by maximum intensity
- Incidence of non-serious TEAEs above threshold of 5% of study participants
- Incidence of non-serious TEAEs above threshold of 5% of study participants by Relationship

Where dates are missing or partially missing, AEs will be assumed to be treatment-emergent, unless there is clear evidence (through comparison of partial dates, see [Section 6.1.6.2](#)) to suggest that the AE started prior to dosing.

Summary tables will contain counts of study participants, percentages of study participants in parentheses and the number of events. A participant who has multiple events in the same SOC and PT will be counted only once in the participant counts, but all events will be included. For the summary of injection site reactions, the specific PTs to be included will be reviewed and documented at the DEM.

In summaries including intensity, the following intensity categories will be summarized: 'Mild', 'Moderate', 'Severe'. Study participants who experience the same event multiple times will be included in the most severe category for tabulations by maximum intensity. Events with missing intensity will be considered as 'Severe' events for summary purposes but recorded as missing in the listings.

In summaries including relationship to CZP, the following relationships will be summarized: 'Not related', 'Related'. Study participants who experience the same event multiple times will be included in the most related category for tabulations by maximum relationship. Events with missing relationship (for CZP) will be considered as 'Related' for the tabulations but recorded as missing in the listings.

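### Treatment-emergent events are defined by start date alone, so an AE recorded in Screening that keeps its onset date and worsens or becomes serious after CZP is left out of the secondary safety tables

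*SAP*

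**What the plan says.** Protocol 9.3 states: "Treatment-emergent AEs will be defined as events that have a start date on or following the first administration of study treatment in RA0138", ending 70 days after the last dose. SAP 5.4.1.2.2 repeats the rule, with a TEAE "defined as events that have a start date on or following the first administration of study treatment in RA0138". Neither mentions an event that begins before dosing and later worsens.

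For serious events, SAP 5.4.1.2.2 says "The treatment-emergent serious adverse event (TESAE) will follow the same definition and also mark serious adverse event as" yes on the AE form. The date on which an event becomes serious is not used.

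SAP 5.4.1.1 gives the key secondary safety endpoint as "treatment emergent SAEs and AEs leading to withdrawal from the time of the first CZP dose through the SFU Visit". SAP 5.4.1 and 5.4.1.2.3 make clear that the withdrawal part is also restricted to treatment-emergent events. For the remaining AE tables, SAP 5.5.1.3 points back: "The definitions of TEAE can be found in" Section 5.4.1.2.2. SAP 6.1.7 draws the special-interest subsets from TEAEs or serious TEAEs.

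On collection, Protocol 8.3.1 starts at signature of the consent form and makes reportable "all AEs that recurred or worsened after the initial visit". On follow-up, Protocol Appendix 3 says "New or updated information will be recorded in the originally completed CRF".

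**The concern.** A treatment-emergent definition should capture what changes after exposure. One based on start date does so for new events, but not for an event already in the database at the first dose that then gets worse. Here the protocol creates such events by collecting AEs through Screening, and it treats worsening as reportable, yet neither document says how the worsening enters the treatment-emergent set.

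The error runs in one direction: it can only lower the count. It reaches every table built on the definition, including the two safety components of the secondary endpoint.

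It also sits oddly beside the SAP's cautious handling elsewhere. SAP 5.5.1.3 treats an AE with a missing or partial date as treatment-emergent unless there is clear evidence of a pre-dose start, a missing intensity as severe, and a missing relationship as related. A vaguely dated event is counted, while a precisely dated one that turns serious on CZP is not.

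**Working it through.** The plan gives no figure that depends on this definition, so there is none to reproduce. The check applies the rule as written and then asks what one event is worth.

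**Inputs**
- First dose on Day 0 and last planned dose on Day 168 (Schedule of Activities; SAP 5.1.1.1.3).
- Screening up to 28 days, Day -28 to Day -1 (SAP 5.1.1.1.3).
- Window end: last dose + 70 days, so 168 + 70 = Day 238 (Protocol 9.3; SAP 5.4.1.2.2).
- 30 participants enrolled (SAP 1.2.2).
- No hypothesis test (SAP 2).

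**Step 1. Apply the rule.** An event counts if 0 ≤ start day ≤ 238.

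| Event | Rule as written | With a worsening clause |
|---|---|---|
| Starts Day -10, becomes serious Day 20 | not counted | counted |
| Starts Day 20, serious Day 20 | counted | counted |

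The first event carries the serious flag but fails the start-date test, so it is an SAE that is not a treatment-emergent SAE.

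**Step 2. See whether anything re-dates the event.**
- Protocol 8.3.1 makes worsening reportable, but measures it from the initial visit rather than the first dose and gives no onset date for it.
- Protocol Appendix 3 lists exacerbation of a pre-existing condition as meeting the AE definition, but does not say whether an AE already recorded gets a second record.
- Appendix 3 on follow-up points towards updating the existing record.
- The date imputation rules in SAP 6.1.6.2 act only on missing or partial dates.

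Nothing in the documents assigns a new onset date. The CRF Completion Guidelines (Protocol 10.1.6.1) might, but are not among the documents provided.

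**Step 3. Value of one participant at N = 30** (exact Clopper-Pearson 95% intervals).

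| Participants | Incidence | 95% CI |
|---|---|---|
| 0/30 | 0.0% | 0 to 11.6% |
| 1/30 | 3.3% | 0.1 to 17.2% |
| 2/30 | 6.7% | 0.8 to 22.1% |

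**Step 4. How likely is at least one?** The documents give no rate. Taking p as an assumed per-participant probability of such an event, the expected count is 30p and the chance of at least one is 1 − (1 − p)^30.

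| p (assumed) | Expected in 30 | Chance of at least one |
|---|---|---|
| 1% | 0.3 | 26% |
| 2% | 0.6 | 45% |
| 5% | 1.5 | 79% |
| 10% | 3.0 | 96% |

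**The case against.** **The onset date may not be kept.** The Appendix 3 sentence on updates is general follow-up guidance and does not mention onset dates. Protocol 8.3.1 and the exacerbation item in Appendix 3 are compatible with a new record at worsening, which the current rule would count. This stands as a limit: a reader might infer that the documents fix the Screening onset date for every worsened AE, but they only point that way. The plan still does not say which practice applies, so the content of the endpoint depends on an unstated data-entry convention.

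**The most worrying example is largely excluded.** A reader might picture a mild infection in Screening that becomes serious on a TNF inhibitor. Exclusion criterion 4 bars any current sign or symptom suggesting infection, and Protocol 5 and 8 allow no waivers. The Schedule of Activities marks eligibility verification only at Screening, so a later infection could be missed, but that would be an eligibility slip. Infection should not carry the argument; the gap applies to any type of AE.

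**Nothing disappears from the report.** SAP 5.5.1.3 lists all AEs on the Safety Set, treatment-emergent or not, in the same layout as the serious-event listing, with onset, intensity and seriousness. SAP 5.2 tabulates discontinuations due to AEs without a treatment-emergent restriction. This stands: the loss is from the endpoint tables, the treatment-emergent listings and the TEAE-based special-interest tables.

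**The stakes are low.** The study is descriptive and built for PK. This bears on priority and does not make the rule correct.

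**Conclusion.** The concern holds in a limited form. An AE already recorded in Screening, with its pre-dose onset date retained, is left out of the TEAE, treatment-emergent SAE, withdrawal and TEAE-based special-interest tables if it intensifies, becomes serious or leads to withdrawal after the first dose. A condition known only from medical history and first recorded as an AE when it worsens after dosing would have a post-dose start date and is captured.

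The conclusion rests on two conditions: that such an AE occurs, and that data entry keeps its first onset date. The number of events is unknown and probably small; each affected participant is worth 3.3 percentage points.

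Two stronger readings are not supported. One is that these events are lost from the study report; the all-AE listing and the disposition table still show them. The other is that about a tenth of events are affected: 28/(28 + 168 + 70) = 28/266 = 10.5% is the largest share of planned collection time that falls before dosing. It is not an event rate, and it says nothing about how many pre-dose events persist and then worsen.

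The primary PK endpoint is unaffected. The change should be made because the rule as written can undercount a named secondary endpoint and is easily corrected.

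**What to change.** In Protocol 9.3 and SAP 5.4.1.2.2, extend the definition with: *or that started before the first administration and increased in intensity, became serious or led to withdrawal on or after it, through the final administration + 70 days*.

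State that each such worsening is counted once. If the CRF Completion Guidelines already require a new AE record with its own onset date, count only that record and cite the guideline in the SAP. If they do not, use the clause with the existing record. Applying both without this rule would count one worsening twice. Where the two records share an SOC and PT, the participant count would be unchanged under SAP 5.5.1.3, but the event count would be inflated.

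The cost is one clause in each document and a counting sentence in the SAP. TEAE counts may rise slightly. The date of worsening, or of becoming serious, must be available to the programmer; where the CRF does not hold it, the form or its guidelines need a line to collect it.

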#### **5.4.1.2.3 Treatment-emergent AEs leading to withdrawal**

Similarly, the analysis for treatment emergent AEs leading to withdrawal from the time of the first CZP dose through the SFU Visit will be included as follows:

- Incidence of treatment emergent AEs leading to withdrawal
- Incidence of treatment emergent AEs leading to withdrawal by Maximum Intensity
- Incidence of treatment emergent AEs leading to withdrawal by Maximum Relationship

Treatment emergent AE summaries will be ordered by alphabetical SOC and decreasing frequency of PT within SOC in the CZP column for tables including event counts.

A listing will be presented for SS for treatment emergent AE leading to withdrawal and follow the same display of output as described in [Section 5.4.1.2.2](#) . The other similar AE data handling rule will be also followed in [Section 5.5.1.2](#).

#### **5.4.1.3 Sensitivity analysis**

Not applicable.

#### **5.4.1.4 Supplementary analyses**

Not applicable.

#### **5.4.2 Supportive secondary endpoint(s)**

Not applicable.

### **5.5 Tertiary/Exploratory Endpoint(s) Analysis**

Tertiary/Exploratory Endpoint(s) analysis of Other Objects and Endpoints will be performed and consist of following objectives:

- To assess the occurrence of anti-CZP antibodies (utilizing the ECLIA method) over the duration of the study
- To assess the efficacy of CZP
- To evaluate other safety parameters

The endpoints will be as follows:

- ADAAb screening status (positive or negative screen), confirmatory status (positive or negative immunodepletion), and the titer for "positive immunodepletion" samples at each scheduled assessment after first CZP dose through SFU
- Change in Routine Assessment of Patient Index Data 3 (RAPID3) from Baseline to Week 12
- TEAEs, vital signs, and laboratory assessments

The following section will present the endpoints except ECG which are described in [Section 5.6.1.1](#).

.

### 5.5.1.1 Immunological Analyses

Immunogenicity samples will be tested using the ECLIA method. Antibodies to CZP will be evaluated in plasma samples collected from all participants according to the Schedule of Activities.

Plasma samples will be screened for antibodies binding to CZP and the titer of confirmed positive samples will be reported. Other analyses may be performed to further characterize the immunogenicity of CZP.

The incidence of immunogenicity will be summarized by visit, as specified and based on SS.

#### 5.5.1.1.1 Handling of dropouts or missing data

Levels of ADAb that are negative or no titer provided will be regarded as zero (negative) for all individual ADAb figures.

#### 5.5.1.1.2 Anti-drug antibodies

ADAb antibodies will be measured using a tiered assay approach: screening assay, confirmatory assay and titration assay. The ADA status at sample level will be defined in [Table 5-1](#).

A screening cut point will be determined by the bioanalytical laboratory that will be used to determine the status of ADAb as Positive Screen (PS) or Negative Screen (NS). Samples presenting ADAb levels PS are considered “potentially ADAb positive” and will be further evaluated in the confirmatory assay, the result of which will be reported as either “Positive Immunodepletion” (PI) or “Negative Immunodepletion” (NI). Confirmed positive samples (reported as PI) will be titrated, and the titer (reciprocal dilution factor including minimum required dilution) will be reported.

ADAb status at sample level:

ADA positive (ADA b +)	Sample values that are ‘positive screen’ and ‘positive immunodepletion’
ADA negative (ADA b -)	Sample values that are either ‘negative screen’ or ‘positive screen’ and ‘negative immunodepletion’ if corresponding drug levels are equal or below the validated drug tolerance limit of the assay allowing detection of 100 ng/ml ADA or limit dictated by the ADA assay and project needs (e.g. 250 ng/ml).
ADA inconclusive	Sample values that are either ‘negative screen’ or ‘positive screen’ and ‘negative immunodepletion’ but with corresponding drug levels above the validated drug tolerance limit of the assay allowing detection of 100 ng/ml ADA or limit dictated by the ADA assay and project needs (e.g. 250 ng/ml)
Missing	Samples that were not collected per schedule or that could not be tested for ADA status due to inadequate sample volume, mishandling, or errors in sample collection, processing, storage, etc.

Participant Classification:

Confidential

- A participant will be classified as overall positive if at least one post Baseline measurement is ADAb+ (see definition above) (this includes participant who have negative and positive results at baseline)
- A participant will be classified as overall negative if at all post Baseline visits the ADAb status is negative (this includes study participants who have positive and negative results at Baseline)
- A participant will be classified as having classification of ADA status as stated in below [Table 5–2](#) .

